7.6.3.2.1. Optional On-Treatment Tumor Samples

Optional tumor biopsy specimens on study may also be obtained anytime in subjects with accessible tumors to assess intratumoral changes that might be associated with safety, response, or resistance to treatment.

If a subject consents to an on-treatment biopsy, the sample must be collected at peak exposure after the morning epacadostat dose (approximately 2-3 hours after dosing) and a peripheral whole blood sample should be collected at the same time as the biopsy and sent to Incyte or its designee in accordance with the Laboratory Manual.

Additionally, one of the subject's target lesions may be used to collect this sample if it is the most accessible for biopsy.

[REDACTED]

[REDACTED]

[REDACTED]	[REDACTED]	[REDACTED]	[REDACTED]	[REDACTED]
[REDACTED]	[REDACTED]	[REDACTED]	[REDACTED]	[REDACTED]
[REDACTED]	[REDACTED]	[REDACTED]	[REDACTED]	[REDACTED]

[REDACTED]

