- ^h Optional and can be obtained anytime for safety or with confirmed response or progression. If a subject consents to an on-treatment biopsy, the sample must be collected at peak exposure after the morning epacadostat dose (approximately 2-3 hours after dosing) and a peripheral whole blood sample should be collected at the same time as the biopsy. Additionally, one of the subject's target lesions may be used to collect this sample if it is the most accessible for biopsy (see Section 7.6.3.2.1).
- ⁱ Imaging will be performed every 12 weeks scheduled from C1D1.
- ^j If a scan was obtained within 4 weeks before the date of discontinuation, then a scan at treatment discontinuation isn't mandatory. In subjects who discontinue study therapy without confirmed disease progression, a radiologic evaluation should be repeated at the time of treatment discontinuation (ie, date of discontinuation \pm 4 week window).

Table 25: Laboratory Assessments

Visit (Range)	Screening	Treatment Cycles					EOT	Follow-Up	
		C1D1	C1D8	C2D1	Day 1 All Subsequent Cycles	Every 12 Weeks ^a	Discontinuation	Safety Follow-Up Visit 1	Safety Follow-Up Visit 2
		Days -28 to -1	±3 Days	±3 Days	±3 Days	±3 Days	±5 Days	+ 7 Days After Last Dose	42 Days After EOT ±7 Days
Safety and eligibility^b									
Chemistry panel	X ^c			X	X		X	X	X
Liver chemistry tests ^d	X ^c			X	X ^d		X	X	X
Hematology with differential	X ^c			X	X		X	X	X
Coagulation panel (PT, INR, aPTT) ^e	X ^c								
Endocrine function testing	X ^c					X	X		
Urinalysis	X					X	X		
Serum pregnancy or urine ^f	X ^c								
Hepatitis B and C	X								
Pharmacokinetics									
Blood sample for epacadostat PK		X ^g	X ^g	X ^g					
Blood sample for durvalumab PK		X ^h		X ^h					
Immunogenicity									
Immunogenicity assessment		X			X ⁱ		X		X
[REDACTED]		■	■						
[REDACTED]				■					
[REDACTED]		■			■		■		

C1D1 = Cycle 1 Day 1; C1D8 = Cycle 1 Day 8; C2D1 = Cycle 2 Day 1.

^a Pharmacokinetic sample for durvalumab will be drawn at Cycle 5 and every 4 cycles (8 weeks) thereafter (Phase 1 only).

^b All safety laboratory tests will be performed locally.

^c Screening laboratory tests must be performed within 7 days of Cycle 1 Day 1. If performed more than 7 days before Cycle 1 Day, the tests must be repeated and eligibility confirmed before study drug administration on Cycle 1 Day 1.

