7.4.3. RECIST v1.1

Tumor lesions that are located in a previously irradiated area, or in an area subjected to other locoregional therapy, should not be selected as target lesions. Additionally, tumor lesions that will be biopsied should not be selected as target lesions.

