7.6.3.2. Analysis of Tumor Samples

Fresh tumor biopsies (defined as a biopsy specimen taken within 28 days prior to the first dose of study treatment) will be required (except as indicated in the inclusion criteria) at baseline. A biopsy specimen from a sample taken since completion of the most recent prior systemic treatment may be acceptable in lieu of a fresh biopsy with medical monitor approval. Archival tissue should also be submitted if available. If a fresh baseline biopsy is inaccessible, an archival specimen should be submitted.

Biopsies should be performed on lesions that have not been exposed to prior radiation. Exceptions to this requirement for SCCHN subjects may be granted on an individual basis by the medical monitor. Tumor lesions used for biopsy should not be lesions used as RECIST target lesions, unless there are no other lesions suitable for biopsy. If a RECIST target lesion is used for biopsy, the lesion must be ≥ 2 cm in the longest diameter. Details and methods for obtaining, processing, and shipping the fresh tumor biopsy samples will be provided in the Study or Laboratory Manual for the study.

[REDACTED]

Biopsy samples may be used to investigate specific protein expression that can be measured using IHC, flow cytometry, mass spectroscopy, or other similar techniques. Biopsy samples may also be used to investigate molecular signatures. DNA and/or RNA may be extracted from these samples to do somatic mutation analysis and gene expression analysis. Genes to be assayed may include, but not be limited by those with known driver mutations in solid tumors. Potential somatic mutations in tumor samples may be confirmed by assessing the specific sequence change in a normal sample obtained by peripheral blood. Biopsy samples may also be assessed for chromosomal alterations that have been shown to be present in solid tumors. These samples will be analyzed by the sponsor or designee.

Note: The Ventana PD-L1 IHC assay will be used to determine the PD-L1 IHC status in this study. The Ventana IHC analysis will be performed at a Ventana-approved College of American Pathologists/Clinical Laboratory Improvement Act laboratory. To meet the requirement of the FDA approval of a companion diagnostic, sections of the tumor will be retained at Ventana for potential additional studies, as requested by the FDA, to support the test approval.

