9.4. Statistical Analyses

9.4.1. Primary Analyses

Phase 1: The safety and tolerability of epacadostat in combination with durvalumab will be evaluated. See Section 9.4.3 for more details. Descriptive statistics (eg, mean, standard deviation, range) will be derived where appropriate. Subject enrollment, disposition, demographics, and medical history will be summarized at baseline. The rate of DLTs will be summarized for each cohort. Dose exposure and density will be calculated for each cohort. Safety and disease response data will be compared over time to assess change from baseline, during treatment, and follow-up. Pharmacokinetic [REDACTED] data will be analyzed with appropriate standard nonlinear analytic software.

Phases 1 and 2: The proportion of subjects with objective response by mRECIST v1.1 will be summarized. A subject is considered an objective responder as assessed by mRECIST v1.1 if he or she has an overall response of CR or PR at any postbaseline visit. The proportion of responders within each treatment group will be estimated with 95% CIs by treatment group. Confidence intervals will be calculated based on the exact method for binomial distributions.

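### The on-treatment biopsy rule for target lesions is looser than the protocol's general biopsy rule, and nothing visible says how a biopsied target lesion counts in the primary ORR

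*Protocol*

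**What the plan says.** Three places in the protocol deal with biopsy of target lesions.

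- Section 7.4.3, on choosing lesions: "tumor lesions that will be biopsied should not be selected as target lesions".
- Section 7.6.3.2, on tumor samples: "Tumor lesions used for biopsy should not be lesions used as RECIST target lesions, unless there are no other lesions suitable for biopsy". It then adds: "If a RECIST target lesion is used for biopsy, the lesion must be ≥ 2 cm in the longest diameter".
- Section 7.6.3.2.1, on optional on-treatment samples, says that one of the subject's "target lesions may be used to collect this sample if it is the most accessible for biopsy". Table 24 footnote h repeats this permission and refers the site only to 7.6.3.2.1. Neither place mentions a size or requires that other lesions be unsuitable.

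On timing, footnote h describes the sample as follows: "Optional and can be obtained anytime for safety or with confirmed response or progression".

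On the endpoint, Section 7.4.3.3.1 defines PR as a fall of at least 30% from baseline in the sum of target-lesion diameters. Under Section 9.4.1 a subject is a responder if he or she "has an overall response of CR or PR at any postbaseline visit". SAP Section 7.3.1 uses the same definition, and SAP Section 3.3.2 states that confirmation is not needed. Response is investigator-assessed (Protocol Section 1.5.1).

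**The concern.** The condition in 7.6.3.2.1 is weaker than the one in its parent section. A target lesion can be the easiest to reach while another lesion is still suitable. A site following 7.6.3.2.1 may then biopsy the target lesion; a site following 7.6.3.2 may not.

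This matters because target-lesion diameters determine the Phase 2 primary endpoint. Sections 7.4.3 and 7.6.3.2 show that the protocol means to keep biopsies away from those lesions where it can, and Section 4.3 offers tumor-size assessment as an objective endpoint when it discusses avoiding bias. If a target lesion is sampled and later measured as usual, part of any change in its diameter may come from the procedure rather than the treatment. With no confirmation step, one such measurement could decide a subject's response status.

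**Working it through.** **1. The rules applied to the same cases.**

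| Situation on treatment | Section 7.6.3.2 | Section 7.6.3.2.1 and footnote h |
|---|---|---|
| Target lesion is easiest to reach; another lesion is suitable | Not allowed | Allowed |
| Only a target lesion is suitable, 2 cm or more | Allowed | Allowed if it is the easiest to reach |
| Only a target lesion is suitable, under 2 cm | Not allowed | No size stated; unclear whether the parent limit carries over |

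The first row is a direct conflict. The third is an ambiguity.

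**2. Timing.** Table 24 marks the optional sample at Cycle 2 Day 1, which is Day 15 with 14-day cycles. The footnote on that entry allows any time, and SAP Table 5 shows the optional sample under Cycle 1 Day 1. On-study imaging is every 12 weeks from first dose (Section 7.4.2). A biopsy can therefore precede every scheduled post-baseline scan, or follow a response already recorded.

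**3. Loss of diameter that would give a PR.** Required fall = 0.30 × baseline sum S. If true shrinkage is 25%, the extra fall needed is (0.30 − 0.25) × S.

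| Target lesions | S | Fall for PR | Extra fall at 25% true shrinkage |
|---|---|---|---|
| One, 10 mm (smallest measurable non-nodal; relevant only if the 2 cm limit does not apply) | 10 mm | 3 mm | 0.5 mm |
| One, 20 mm | 20 mm | 6 mm | 1 mm |
| Five, 20 mm each | 100 mm | 30 mm | 5 mm |

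Five is the maximum number of target lesions (Section 7.4.3.2).

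**4. The plan's own figures, then the weight of one miscounted response.** For the expansion cohorts (10% vs 30%, one-sided alpha 10%, power 90%), the smallest exact binomial design is 25 subjects with at least 5 responses (alpha 0.098, power 0.9095). Allowing for 10% lost to follow-up, 25/0.9 = 27.8, so 28, which matches Table 34. The Table 33 Simon designs also reproduce (alpha / power): melanoma 0.049 / 0.901, TNBC 0.050 / 0.907, gastric and GE junction 0.035 / 0.902.

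One miscounted response among 28 adds 1/28 = 3.6 percentage points to the ORR.

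In the Simon cohorts, one miscounted response changes the Stage 1 outcome only when the true count is exactly on the cut-off. At P0 the chance of that is:

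- gastric and GE junction: P(X = 1 | n = 9, p = 0.10) = 0.387
- TNBC: P(X = 2 | n = 13, p = 0.15) = 0.294
- melanoma: P(X = 5 | n = 15, p = 0.30) = 0.206

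These are only probabilities of sitting on the cut-off. They hold for a miscount from any cause and say nothing about how often a biopsy produces one.

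As an assumed range, let a fraction f of true non-responders be counted as responders. At a true ORR of 10%, the observed rate is 0.10 + 0.90f. The chance of at least 5 of 25 responses rises from 0.098 to 0.129 (f = 1%), 0.165 (f = 2%) or 0.292 (f = 5%). The documents supply no value of f.

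**5. Handling rules.** Protocol Table 28 returns not evaluable when target lesions are not all evaluated. SAP Section 7.4.4, for the percent-change analysis, assigns 5 mm to a lesion too small to measure and 0 mm to one not present, and makes the sum not evaluable if a lesion is unaccounted for. None of these mentions a biopsied lesion. The only ORR sensitivity analysis in SAP Section 7.3.1 uses a response-evaluable population, which does not address it.

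**The case against.** The strongest reply is that this is one wording tension about an optional procedure, in a single-arm study that tests no formal efficacy hypothesis (Protocol Section 9.3). Much of that is fair.

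- A reader might infer that on-treatment biopsies have no size limit. The documents do not support this: the 2 cm sentence in 7.6.3.2 is worded for any biopsy of a RECIST target lesion, 7.6.3.2.1 sits beneath it, and nothing waives it. What stands is that the on-treatment text does not repeat the limit and footnote h bypasses the section containing it.
- A reader might see a flat contradiction with 7.4.3. That section governs which lesions are selected, and a later optional biopsy may not be foreseen then. The clash with 7.6.3.2 is the firmer one.
- A reader might take Day 15 as the fixed biopsy time. The footnote says otherwise, and a biopsy after a recorded response cannot have created that response.
- A reader might infer that the bias always favors response. The documents give neither technique nor tissue volume, and Section 7.6.3.2 leaves methods to the Study or Laboratory Manual.
- Passing Stage 1 is not a positive result; the total cut-offs in Table 33 still apply.
- Text in 7.6.3.2 and after 7.6.3.2.1 is blacked out, so the lack of a handling rule can be judged only on visible text.

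None of this removes the conflict between 7.6.3.2 and 7.6.3.2.1, or supplies a rule for counting a biopsied target lesion.

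**Conclusion.** The point holds as an inconsistency to reconcile and a gap in endpoint handling. Section 7.6.3.2.1 and Table 24 footnote h permit on-treatment biopsy of a target lesion on a weaker condition than 7.6.3.2, and it is unclear whether the 2 cm limit applies. Because the biopsy can precede the first on-study scan and an unconfirmed response at any visit counts, an altered target lesion could change a subject's status in the primary ORR.

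The effect is possible, not shown. It matters most with one or few small target lesions, or when true shrinkage is already near 30%, and least with several large ones. Each miscounted subject would shift a 28-subject cohort by 3.6 points. The number of such subjects is unknown, since the documents give no rate of on-treatment biopsies. The 2 cm limit would reduce the exposure without removing it. The change is worth making because it applies the protocol's own rule and costs little.

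**What to change.** 1. In Section 7.6.3.2.1 and Table 24 footnote h, replace the accessibility condition with the conditions already in 7.6.3.2: a non-target lesion first, a target lesion only if no other is suitable, and the 2 cm limit stated to apply on treatment. Cross-reference 7.4.3, and point footnote h to 7.6.3.2 as well.
2. On the lesion CRF page, flag any target lesion biopsied after baseline, with the date.
3. In the SAP, add one ORR sensitivity analysis that counts as non-responders those subjects whose first CR or PR came after biopsy of a target lesion and depends on that lesion. State in advance how dependence is judged, for example by recalculating the baseline and follow-up sums without the lesion.

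The cost is two short text changes, a cross-reference, one CRF field and one analysis line. A few optional on-treatment biopsies may be lost or taken from a less accessible lesion. The flag and the sensitivity analysis remain useful for subjects already enrolled, provided biopsy sites and dates can be recovered from source records.

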7.7. Other Study Procedures

7.7.1. Dispensing of Study Drug

7.7.1.1. Dispensing of Epacadostat

An initial bulk supply of epacadostat will be provided to investigative sites prior to enrollment of the first subject. Thereafter, the site staff will contact the sponsor for resupply of epacadostat. When dispensing to subjects, the investigator or designee will remove the appropriate quantity of epacadostat from their stock, dispense the medication, and enter the amount dispensed into the CRF and drug accountability log. Full details will be provided in the Study Manual.

7.7.1.2. Dispensing of Durvalumab

An initial bulk supply of durvalumab will be provided to investigative sites prior to enrollment of the first subject. Thereafter, the site will contact the sponsor for resupply of durvalumab. The investigator or designee will calculate the number of durvalumab vials needed, pull the appropriate number of vials to prepare the infusion solution, and enter the vials used into the CRF and drug accountability log. Full details will be provided in the Study Manual.

7.7.2. Administration of Study Drug

7.7.2.1. Administration of and Compliance With Epacadostat

Subjects will take their dose of epacadostat morning and evening, approximately 12 hours apart without regard to food. Subjects will self-administer epacadostat except on Cycle 1 Day 1, Cycle 1 Day 8 (Phase 1 only), and Cycle 2 Day 1, when the morning dose will be given at the study site clinic.

Epacadostat compliance will be calculated by the sponsor based on the drug accountability documented by the site staff and monitored by the sponsor/designee (tablet counts). The objective is 100% compliance, and investigators and their staff should evaluate compliance at each visit and take appropriate steps to optimize compliance.

7.7.2.2. Administration of and Compliance With Durvalumab

Administration of durvalumab will be witnessed by the investigator and/or study staff. The total volume of study treatment infused will be compared to the total volume prepared to determine compliance with each dose administered.

The instructions for preparing and administering durvalumab are described in a separate pharmacy manual.

7.7.3. Distribution of Subject Reminder Cards and Diaries

Subjects will be provided with reminder cards at each visit. The subject reminder cards will indicate the date/time of the next visit, and will also remind the subject when they should not take their morning dose of study drug and when they should arrive for the visit after an overnight fast of at least 8 hours or since midnight. On Day 1 only, subjects will also be given SS information sheet for signs and symptoms of SS. This information sheet also instructs subjects to seek immediate medical care if any of these symptoms are observed.

8. SAFETY MONITORING AND REPORTING

8.1. Adverse Events

8.1.1. Definitions and Reporting

For the purposes of this Protocol, an AE is defined as the appearance of (or worsening of any pre-existing) undesirable sign(s), symptom(s), or medical condition(s) that occur after a subject provides informed consent. Abnormal laboratory values or test results occurring after informed consent constitute AEs only if they induce clinical signs or symptoms, are considered clinically meaningful, require therapy (eg, hematologic abnormality that requires transfusion), or require changes in the study drug(s).

Adverse events that begin or worsen after informed consent should be recorded on the Adverse Events page of the CRF. Conditions that were already present at the time of informed consent should be recorded on the Medical History page of the CRF. Adverse event monitoring should be continued for at least 90 days after the last dose of study treatment. Adverse events (including laboratory abnormalities that constitute AEs) should be described using a diagnosis whenever possible rather than by individual underlying signs and symptoms. When a clear diagnosis cannot be identified, each sign or symptom should be reported as a separate AE.

Adverse events will be assessed according to the CTCAE version 4.0. The CTCAE severity Grade 5 (death) will not be used in this study; rather, information about deaths will be collected as an outcome of the event. The occurrence of AEs should be sought by nondirective questioning of the subject during the screening process after signing the ICF and at each visit during the study. Adverse events may also be detected when they are volunteered by the subject during the screening process or between visits, or through physical examination, laboratory test, or other assessments. As far as possible, each AE should be evaluated to determine:

- The severity grade (CTCAE Grade 1 to 4).
- Reasonable possibility that the AE is related to the study treatment: unrelated (no) or related (yes).

NOTE: Since this is a combination study of epacadostat with durvalumab, the relationship to study drug can be assessed for epacadostat alone, durvalumab alone, the combination of epacadostat with durvalumab, or not related to either epacadostat or durvalumab.

- Start and end dates, unless unresolved at final examination.
- Action taken with respect to study drug (eg, none, dose adjusted, temporarily interrupted, permanently discontinued, unknown, not applicable).
- Outcome (eg, not recovered/not resolved, recovered/resolved, recovering/resolving, recovered/resolved with sequelae, fatal, unknown).
- Whether it is serious, as per SAE definition provided in Section 8.3.1.

Unlike routine safety assessments, SAEs are monitored continuously and have special reporting requirements, see Section 8.3.2.

All AEs should be treated appropriately. If a concomitant medication or nondrug therapy is given, this action should be recorded on the AE and Prior/Concomitant medications pages of the CRF.

Once an AE is detected, it should be followed until it has resolved or until it is judged to be permanent; assessment should be made at each visit (or more frequently if necessary) of any changes in severity, the suspected relationship to the study drug, the interventions required to treat it, and the outcome.

Disease progression should not be regarded or reported as an AE itself, unless it is associated with a separate AE.

8.2. Laboratory Test Abnormalities

8.2.1. Definitions and Reporting

Laboratory abnormalities that constitute an AE in their own right (are considered clinically meaningful, induce clinical signs or symptoms, require concomitant therapy, or require changes in study drug), should be recorded on the AE page of the CRF. Whenever possible, a diagnosis rather than a symptom should be provided (eg, anemia instead of low hemoglobin). Laboratory abnormalities that meet the criteria for AEs should be followed until they have returned to normal or an adequate explanation of the abnormality is found. When an abnormal laboratory test result corresponds to a sign or symptom of a previously reported AE, it is not necessary to separately record the laboratory test result as an additional event.

Laboratory abnormalities that do not meet the definition of an AE should not be reported as AEs. A Grade 3 or 4 (severe) AE, as per CTCAE, does not automatically indicate an SAE unless it meets the definition of serious, as defined in Section 8.3.1, and/or per the investigator's discretion. A dose interruption or adjustment for the laboratory abnormality may be required (see Section 5.6) and should not contribute to the designation of a laboratory test abnormality as an SAE.

8.2.2. Potential Drug-Induced Liver Injury (or Hy's Law)

Wherever possible, timely confirmation of initial liver-related laboratory abnormalities should occur prior to the reporting of a potential DILI event (also known as Hy's Law). All occurrences of potential DILIs, meeting the defined criteria, must be reported as SAEs (see Section 8.3.2 for reporting details).

Potential drug induced liver injury is defined as:

1. AT (ALT or AST) elevation > 3 times ULN
AND
2. Total bilirubin > 2 times ULN, without initial findings of cholestasis (elevated serum alkaline phosphatase),
AND
3. No other immediately apparent possible causes of AT elevation and hyperbilirubinemia, including, but not limited to, viral hepatitis, pre-existing chronic or acute liver disease, or the administration of other drug(s) known to be hepatotoxic.

